2.5.3 Handling of intercurrent events

The remaining intercurrent event of the primary estimand for the two primary efficacy variables are the following:

1. Potential use of inclisiran by participants in the usual care group. This intercurrent event will be ignored in the analysis, as the design of the trial allows for participants in the usual care group to potentially use inclisiran.
2. Discontinuation of study treatment (in inclisiran + usual care participants). This intercurrent event will be ignored in the analysis.
3. Use of prohibited medication (monoclonal antibodies directed against PCSK9, as defined in [Table 2-3](#)) in the inclisiran + usual care group. This intercurrent event will be ignored in the analysis.

2.5.4 Handling of missing values not related to intercurrent event

For the primary analysis of primary efficacy variable 1, the MMRM implicitly imputes missing data under a missing at random assumption.

For the primary analysis of primary efficacy variable 2, participants with missing LDL-C data will be assumed to have LDL-C \geq 70 mg/dL (i.e., “non-responder”).

2.5.5 Sensitivity analyses

The sensitivity analysis of primary efficacy variable 1 to address the primary objective will be based on the following estimand:

- Population: Defined through appropriate inclusion/exclusion criteria to reflect the targeted population
- Variable: Percent change from baseline in LDL-C [The primary analysis time point is at Day 330.]
- Treatment: Inclisiran + usual care or usual care
- Remaining intercurrent events: 1. Potential use of inclisiran by participants in the usual care group. This intercurrent event will be ignored in the analysis, as the design of the trial allows for participants in the usual care group to potentially use inclisiran. 2. Discontinuation of study treatment. This intercurrent event will be ignored in the analysis. 3. Use of prohibited medication (monoclonal antibodies directed against

PCSK9, as defined in [Table 2-3](#)) in the inclisiran + usual care group. This intercurrent event will be ignored in the analysis.

- Summary measure: Probability of observing the same or a more favorable response with inclisiran + usual care relative to usual care

For the above estimand, primary efficacy variable 1 will be analyzed at each time point for the FAS using the Wilcoxon rank-sum test.

The probability of observing the same or a more favorable response (θ_0) with inclisiran + usual care relative to usual care will be estimated using nonparametric methods, and the associated two-sided 97.5% confidence interval will also be reported ([Chen and Kianifard 2000](#)).

The sensitivity analysis of primary efficacy variable 2 to address the primary objective will be based on the following estimand:

- Population: Defined through appropriate inclusion/exclusion criteria to reflect the targeted population
- Variable: Achieving LDL-C < 70 mg/dL (yes, no) [The primary analysis time point is at Day 330.]
- Treatment: Inclisiran + usual care or usual care
- Remaining intercurrent events: 1. Potential use of inclisiran by participants in the usual care group. This intercurrent event will be ignored in the analysis, as the design of the trial allows for participants in the usual care group to potentially use inclisiran. 2. Discontinuation of study treatment. This intercurrent event will be ignored in the analysis. 3. Use of prohibited medication (monoclonal antibodies directed against PCSK9, as defined in [Table 2-3](#)) in the inclisiran + usual care group. This intercurrent event will be ignored in the analysis.
- Summary measure: Treatment difference ($[\text{inclisiran + usual care}] - \text{usual care}$) in the proportion of participants who achieve LDL-C < 70 mg/dL

For the above estimand, primary efficacy variable 2 will be analyzed at each post-baseline visit for the FAS using the two-sample z-test (normal approximation to the binomial distribution) to compare inclisiran + usual care versus usual care. Two-sided 97.5% confidence intervals will be calculated, using the normal approximation to the binomial distribution.

For both primary efficacy variables 1 and 2, additional sensitivity analyses will be conducted by repeating the corresponding primary analyses on participants in the Full Analysis Set but excluding participants with baseline LDL-C < 70 mg/dL.

2.5.6 Supplementary analyses

A supplementary analysis of primary efficacy variable 1 will be based on the following estimand:

- Population: Defined through appropriate inclusion/exclusion criteria to reflect the targeted population
- Variable: Percent change from baseline in LDL-C [The primary analysis time point is at Day 330.]

- Treatment: Inclisiran + usual care or usual care
- Remaining intercurrent events: 1. Potential use of inclisiran by participants in the usual care group. 2. Discontinuation of study treatment. 3. Use of prohibited medication (monoclonal antibodies directed against PCSK9, as defined in [Table 2-3](#)) in the inclisiran + usual care group. Data after the occurrence of either one of the above three intercurrent events will be excluded from the analysis (using MMRM).
- Summary measure: Least-squares mean difference between inclisiran + usual care group and usual care group

A supplementary analysis of primary efficacy variable 2 will be conducted by repeating the primary analysis based on observed LDL-C values per visit. Missing data will not be imputed. Therefore, the denominator for deriving the proportion of participants achieving LDL-C <70 mg/dL will be the number of participants with non-missing LDL-C per visit and treatment group.

2.5.7 Subgroup analyses

The primary analysis for primary efficacy variables 1 and 2 will be repeated for subgroups of participants according to the subgroup categories defined in [Section 2.2.1](#). To this end, the same approach as defined in [Section 2.5.2](#) for the primary analysis will be applied separately to the sets of participants within each subgroup category. Note that results for a subgroup category will only be presented if the total across both treatment groups within the category is at least 10 participants.

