5.1 Inclusion criteria

Participants eligible for inclusion in this study must meet all of the following criteria:

- 1. Males and females ≥18 years of age
- 2. Recent ACS (in-patient/out-patient) within 5 weeks of screening, defined as: Ischemic symptoms with unstable pattern, occurring at rest or minimal exertion within 24 hours of an unscheduled hospital admission or emergency department visit, due to presumed or proven obstructive coronary disease AND at least one of the following:
 - a. Elevated cardiac biomarkers (cardiac troponin (cTn) or the MB fraction of creatinine kinase (CKMB)) with at least one value above the 99th percentile of the upper reference limit (URL) or defined by the local laboratory MI diagnosis cut-off values OR
 - b. Resting ECG changes consistent with ischemia or infarction AND additional evidence of obstructive coronary disease
- 3. Serum LDL-C \geq 70 mg/dL or non-HDL-C \geq 100 mg/dL
- 4. Fasting triglycerides <4.52 mmol/L (<400 mg/dL) at screening
- 5. Calculated glomerular filtration rate >20 mL/min by estimated glomerular filtration rate (eGFR)
- 6. Participants must be willing and able to give informed consent before initiation of any study related procedures and willing to comply with all required study procedures
- 7. Participants are required to be on statin therapy, or have documented statin intolerance, as determined by the investigator, following hospitalization (in-patient/outpatient) for an ACS. Statin intolerant patients are eligible if they had intolerable side effects on at least 2 different statins, including one at the lowest standard dose.

5.2 **Exclusion criteria**

Participants meeting any of the following criteria are not eligible for inclusion in this study.

- 1. Any uncontrolled or serious disease, or any medical or surgical condition, that may either interfere with participation in the clinical study, and/or put the participant at significant risk (according to investigator's [or delegate] judgment) if he/she participates in the clinical study.
- 2. An underlying known disease, or surgical, physical, or medical condition that, in the opinion of the investigator (or delegate) might interfere with interpretation of the clinical study results.
- 3. New York Heart Association (NYHA) class IIIb or IV heart failure or last known left ventricular ejection fraction <25%.

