2.2.1 Subgroup of interest

Subgroup analyses of the two primary efficacy variables and the secondary endpoint of absolute change from baseline in LDL-C will be performed for the following subgroups (note that results for a subgroup category will only be presented if the total across both treatment groups within the category is at least 10 participants):

- Background lipid-lowering therapy at baseline: Yes, No
- Medical history of statin intolerance: Yes, No (from medical history statin intolerance CRF page)
- Baseline statin intensity: High, Moderate or Low, None
- Age: <65 years, >= 65 years
- Sex: Male, Female
- Race subgroup 1: White, Non-White/Multiple (unknown will be excluded from subgroup analyses)
- Race subgroup 2: White, Black or African American, Non-White/Non-Black or African American/Multiple (unknown will be excluded from subgroup analyses)
- Ethnicity: Hispanic or Latino, Not Hispanic or Latino (unknown or not reported will be excluded from subgroup analyses)
- BMI: >=30 vs < 30, and >=25 vs < 25 kg/m²
- Renal impairment by eGFR categories at baseline: <15, ≥15 to <30, ≥30 to <60, ≥60 to <90, or ≥90 mL/min/1.73m²
- Baseline LDL-C: <=100 and > 100 mg/dL; by median; and then by quartiles
- Index myocardial infarction: ST segment elevation myocardial infarction (STEMI), Non-ST-segment elevation myocardial infarction (NSTEMI), No myocardial infarction (from ACS medical history)
- Atrial fibrillation associated with index myocardial infarction: Yes, No (from ACS medical history)
- Revascularization procedure during index ACS event: Yes, No (from ACS medical history)
- History of diabetes: Yes, No (from ACS medical history)
- Baseline glycemic status: Diabetes, Pre-diabetes, Normoglycemia

For definition of baseline glycemic status, refer to Section [2.7.3, Table 2-4](#).

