2.5.2 Statistical hypothesis, model, and method of analysis

Primary efficacy variable 1

The null hypothesis is that the mean percent change from baseline in LDL-C at Day 330 for inclisiran + usual care and usual care treatment groups are equal. The alternative hypothesis is that the mean percent change from baseline in LDL-C at Day 330 for inclisiran + usual care treatment group is not equal to that of the usual care treatment group.

Primary efficacy variable 1 will be analyzed using mixed-effects model repeated measures (MMRM) with treatment, visit (Day 90, Day 270, Day 330), baseline, treatment-by-visit interaction, and baseline-by-visit interaction as explanatory variables. An unstructured covariance matrix will be assumed for this model. Least-squares mean of each treatment group, least-squares mean treatment difference, two-sided 97.5% confidence intervals for the treatments, two-sided 97.5% confidence interval for the treatment difference, and p-value based on the fitted MMRM will be reported for each applicable visit (day). If the p-value based on a two-sided test for treatment at Day 330 is < 0.025 and the corresponding least squares mean treatment difference ([inclisiran + usual care] - usual care) is less than 0, statistical significance in favor of inclisiran + usual care is shown. All efforts will be made to follow up participants until the end of the study. Participants will be expected to follow the visit schedule and assessments even after discontinuation of study treatment. Data after participants discontinued study treatment will be used in the analysis ("retrieved dropout"). In case of non-convergence of a model while using an unstructured covariance matrix, compound symmetry will be tried instead.

The primary analysis of primary efficacy variable 1 will be based on the FAS. The primary analysis of this variable will be repeated for the Per-Protocol Set, Restricted Set 1, and Restricted Set 2.

Primary efficacy variable 2

Let π_j denote the probability of achieving LDL-C < 70 mg/dL at Day 330 for treatment group j , $j = 0, 1$, where 0 corresponds to usual care and 1 corresponds to inclisiran + usual care. Accordingly, $\pi_j/(1 - \pi_j)$ is the odds for treatment group j , $j = 0, 1$.

The following null hypothesis (H_0) will be tested against the alternative hypotheses (H_A), corresponding to the comparison inclisiran + usual care versus usual care:

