2.6.6 Subgroup analyses

The analysis for secondary efficacy variable 1 (absolute change from baseline in LDL-C) will be repeated for subgroups of participants according to the subgroup categories defined in Section 2.2.1. To this end, the same approach as defined in Section 2.6.2 for the analysis of secondary efficacy variable 1 will be applied separately to the sets of participants within each subgroup category. Note that results for a subgroup category will only be presented if the total across both treatment groups within the category is at least 10 participants.

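### Subgroup results come from separate models with no treatment-by-subgroup estimate, and the display floor of 10 participants is pooled over both arms

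*SAP*

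**What the plan says.** SAP 2.2.1 lists the subgroup factors for "Subgroup analyses of the two primary efficacy variables and the secondary endpoint of absolute change from baseline in LDL-C". SAP 2.5.7 says that the primary approach is "applied separately to the sets of participants within each subgroup category", and SAP 2.6.6 says the same for absolute LDL-C change. The display rule, given in 2.2.1, 2.5.7 and 2.6.6, is that "results for a subgroup category will only be presented if the total across both treatment groups within the category is at least 10 participants".

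The MMRM that is refitted (SAP 2.5.2) has treatment, visit and baseline, with "treatment-by-visit interaction, and baseline-by-visit interaction as explanatory variables", and "An unstructured covariance matrix will be assumed for this model". If it does not converge, compound symmetry is tried. The logistic model falls back to Firth's method and then may drop baseline LDL-C.

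SAP 1.1 states that randomization is unstratified. On subgroup size, SAP section 3 says only that the total allows subgroups of reasonable size to be examined. Neither document plans a treatment-by-subgroup term or a contrast between categories, and neither calls the subgroup results exploratory. Protocol 12.4.6 does place them under supplementary analysis.

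**The concern.** There are two separate issues.

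**Comparison.** Subgroup tables are read to see whether the effect differs between categories. Separate fits give one effect per category and leave that question to side-by-side reading. One category reaching significance while another does not is weak evidence of a difference. The fallbacks add to this: small categories are the likeliest to trigger them, so effects for one factor may come from different covariance structures, or from an adjusted odds ratio beside an unadjusted one.

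**Display floor.** Ten in total can mean very few in one arm, because nothing controls balance within a category. The floor also counts participants rather than those with data, while the plan assumes 20% loss by Day 330. Some small categories are foreseeable. Entry requires statin therapy or documented intolerance, and an eGFR above 20 (Protocol 5.1). Yet the list includes no background lipid-lowering therapy, no statin and, under "Renal impairment by eGFR categories at baseline", bands of <15 and 15 to <30.

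**Working it through.** **Inputs** (SAP section 3): SD 40, difference 15, two-sided alpha 0.025 per primary variable, power 0.85, 1:1 allocation, responder proportions 0.55 and 0.75, 20% loss.

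**Plan's own figure.** Per arm: 2 × (2.241 + 1.036)² × 40² / 15² = 152.8, so 153 per arm and 306 in total. With loss: 153 / 0.8 = 191.25, so 192 per arm and 384 in total. Both match the SAP.

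**Number of results.** In the order of SAP 2.2.1: 2 + 2 + 3 + 2 + 2 + 2 + 3 + 2 + 4 (BMI) + 5 (eGFR) + 8 (LDL-C) + 3 + 2 + 2 + 2 + 3 = 47 categories. Three endpoints give at most 141 results.

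**Model size.** Fixed effects: intercept 1, treatment 1, visit 2, baseline 1, treatment-by-visit 2, baseline-by-visit 2 = 9. An unstructured covariance over three visits adds 6. Ten participants supply at most 30 observations.

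**Precision of percent change in LDL-C** (single-visit approximation to the MMRM; half-width = critical value × 40 × √(1/n₁ + 1/n₂)):

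| Split | SE | 97.5% half-width, normal | 97.5% half-width, t on n − 3 df |
|---|---|---|---|
| 5 v 5 | 25.3 | 56.7 | 71.9 |
| 4 v 4 (20% lost) | 28.3 | 63.4 | 89.5 |
| 8 v 2 | 31.6 | 70.9 | 89.8 |
| 10 v 10 | 17.9 | 40.1 | 44.0 |
| 20 v 20 | 12.6 | 28.4 | 29.6 |
| 48 v 48 | 8.2 | 18.3 | 18.6 |
| 96 v 96 | 5.8 | 12.9 | 13.0 |

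At 5 v 5 the half-width is 3.8 to 4.8 times the planned effect. With an SD of 30 to 50, the normal half-width runs from 42.5 to 70.9. A half-width of 15 needs 2 × (2.241 × 40 / 15)² = 71.5, so about 72 per arm.

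**Arm imbalance.** The chance that one arm has two or fewer of 10 is 2 × (1 + 10 + 45) / 1024 = 10.9%. The same formula gives 3.9% at 12 participants, 0.7% at 15 and 0.04% at 20.

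**Odds ratio at 5 v 5, planned proportions.** OR = (0.75/0.25) / (0.55/0.45) = 2.45. Variance of the log OR = 1/2.75 + 1/2.25 + 1/3.75 + 1/1.25 = 1.875, so the 97.5% interval is exp(0.898 ± 2.241 × 1.369) = 0.11 to 52.8. The chance that at least one arm is all or no responders is 1 − (1 − 0.75⁵ − 0.25⁵)(1 − 0.55⁵ − 0.45⁵) = 29%.

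**Side-by-side reading with identical true effects** (306 evaluable, 50/50 split). Each category has 76.5 per arm, so SE = 40 × √(2/76.5) = 6.47. Power is Φ(15/6.47 − 2.241) = 0.53. The chance that exactly one category is significant is 2 × 0.53 × 0.47 = 50%. The same method gives 60% for a 25/75 split and 74% for 10/90.

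**Interaction estimate, same 50/50 split.** SE = 40 × √(4/153 + 4/153) = 9.15 and the 95% half-width is 1.96 × 9.15 = 17.9. Power for a 15-point difference in effect at two-sided 0.05 is Φ(15/9.15 − 1.96) = 37%. For a 10/90 split, SE is 15.2, the half-width 29.9 and power 16%.

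**The case against.** Reporting within-category effects with intervals is a legitimate descriptive choice. A display floor exists, convergence fallbacks are prespecified, and the protocol treats subgroups as supplementary. All of that stands, but the fallbacks deal with convergence and not with precision or comparability.

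A reader might infer that subgroup intervals in general will be unusable. The documents do not support that. The 57-to-72-point figure belongs to a category at the floor, and no expected category sizes are given. The baseline LDL-C median split should give about 96 per arm and the quartiles about 48 per arm, with half-widths near 13 and 18 points.

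A reader might also infer that categories cannot validly be compared. That is too strong: categories within a factor are disjoint and their estimates independent, so a difference and its interval follow from the reported results. What is missing is a planned contrast.

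Nor is 141 an expected count. The White category appears in both race groupings, other splits overlap, and the <15 eGFR band should be empty or nearly so and would be suppressed. The 97.5% half-width does not apply to absolute LDL-C change, which is in mg/dL with 95% intervals.

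Lastly, the remedy has limits. Ten per arm still gives about 40 to 44 points, and the interaction has low power.

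**Conclusion.** The point holds as a low-severity improvement. The plan specifies no estimate of how the treatment effect differs between categories, and its pooled floor allows model-based results for categories that are close to inestimable in one arm. At the floor the half-width is about 57 to 72 points against a planned effect of 15, with an 11% chance at exactly 10 participants of two or fewer in one arm. Both problems fade quickly as categories grow. The lack of a planned contrast applies to categories of any size.

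These figures rest on the plan's SD of 40, a single-visit approximation to the MMRM and 1:1 allocation. How many categories will fall near 10 is unknown. The primary analysis, alpha split and sample size are not affected, and nothing in the documents plans a claim of differing effect.

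**What to change.** In SAP 2.5.7 and 2.6.6, fit one Full Analysis Set model per subgroup factor with a treatment-by-subgroup interaction (by visit for the MMRM). Report each category effect and the interaction estimate with its confidence interval from that model, and label the results exploratory.

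Replace the pooled floor in 2.2.1, 2.5.7 and 2.6.6 with a per-arm minimum of participants who have an LDL-C value at the analysis visit, and give descriptive statistics only below it. Ten per arm is an example that protects estimability, not precision.

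The cost is a modest SAP and programming change with no new data. The single model assumes a common covariance across categories, which separate fits do not. At 5 v 5 the resulting larger error degrees of freedom bring the half-width from about 72 to about 57 points and no lower. Very small categories lose their model-based result. Because interaction power is about 37% for a 15-point difference even at a 50/50 split, the interaction should be read as an estimate with its interval and not as a test.

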2.6 Analysis supporting secondary objectives

The secondary efficacy objectives include the following:

- To assess (1) the absolute change from baseline in LDL-C level by visit, and (2) average of percent and absolute changes from baseline in LDL-C levels to each post-baseline visit, in the inclisiran + usual care group compared to usual care group at Day 330
- To assess the proportion of participants reaching pre-specified LDL-C targets in the inclisiran + usual care group compared to usual care group at Day 330
- To assess plasma lipoproteins and triglycerides in the inclisiran + usual care group compared to usual care group at Day 330
- To assess changes in and adherence to background lipid-lowering therapy in the inclisiran + usual care group compared to usual care group at Day 330

2.6.1 Secondary endpoint(s)

The secondary efficacy variables are the following:

1. Absolute change from baseline in LDL-C
2. Average percent change from baseline in LDL-C levels to each post-baseline visit
3. Average absolute change from baseline in LDL-C levels to each post-baseline visit

4. Achieving LDL-C < 100 mg/dL (yes, no) (among the subset of participants with LDL-C \geq 100 mg/dL at baseline)
5. Achieving \geq 50% reduction from baseline in LDL-C (yes, no)
6. Achieving LDL-C < 55 mg/dL (yes, no)
7. Percent change from baseline in apoB
8. Absolute change from baseline in apoB
9. Percent change from baseline in VLDL
10. Absolute change from baseline in VLDL
11. Percent change from baseline in non-HDL-C
12. Absolute change from baseline in non-HDL-C
13. Percent change from baseline in total cholesterol
14. Absolute change from baseline in total cholesterol
15. Percent change from baseline in Lp(a)
16. Absolute change from baseline in Lp(a)
17. Percent change from baseline in HDL-C
18. Absolute change from baseline in HDL-C
19. Percent change from baseline in triglycerides
20. Absolute change from baseline in triglycerides
21. Intensity of lipid-lowering therapy (decrease in dose, no change in dose, increase in dose)

Intensity of therapy is only available for statins, not for other lipid-lowering therapies used in this study. Therefore, for each participant and analysis visit, the highest statin intensity on each nominal visit date will be compared to baseline statin intensity. The decrease, no change, and increase in statin intensity at each visit will be assigned as follows:

Statin Intensity		Post-baseline Visit			
Baseline		High	Moderate	Low	None
	High	No change	Decrease	Decrease	Decrease
	Moderate	Increase	No change	Decrease	Decrease
	Low	Increase	Increase	No change	Decrease
	None	Increase	Increase	Increase	No change

22. Proportion of days covered (total number of days on either statin, ezetimibe, or PCSK9 inhibiting monoclonal antibody therapies divided by total number of study days)

If a participant did not take any of the three medications, then the total number of days will be assumed to be zero. Total number of study days is the total study duration (not treatment duration).

23. Discontinuation of statin therapy (i.e., no statin use \geq 30 days before the end-of-study visit) (yes, no)

If a participant is considered a study completer and has a non-missing visit date for the nominal Day 330 visit recorded, a statin assessment date (to assess if the participant was taking statins at this point in time) will be calculated by subtracting 30 days from the Day 330 visit date (e.g., study Day 300 if the participant completes on study Day 330). The statin assessment date will be compared to the maximum statin end date of all statin medications taken by the participant. If the last statin is recorded as ongoing at study end date, the maximum statin end date will be set to the study end date.

If the participant was on a statin on or after this statin assessment day (maximum statin end date \geq statin assessment date), the participant will be considered as discontinued statin = 'no'.

If the participant was not on a statin on and after this statin assessment day (maximum statin end date $<$ statin assessment date), or they were a completer who did not have a Day 330 visit, the participant will be considered as discontinued statin = 'yes'.

All early termination participants will be considered to not be on a statin for this endpoint (the participant will be considered as discontinued statin = 'yes').

Participants who were not taking any statin while on study will be considered to not be on a statin for this endpoint (the participant will be considered as discontinued statin = 'yes').

The analysis will be based on the FAS excluding participants who had medical history of statin intolerance.

